EA1131 will also offer unique access to a population of relatively young women with breast cancer. In PrECOG 0105, the median age was 48 years (range 26-73), and roughly 60% of participants were premenopausal. Patients enrolling on EA1131 may be even younger, as oncologists will preferentially elect to refer younger women and/or younger women may be the most desirous of further treatment. Thus, we expect that EA1131 will have a median age of at least 48 or possibly younger, with the majority (60% or more) being premenopausal at breast cancer diagnosis. This presents a number of unique considerations, given that these young women may live for decades after diagnosis if they do not succumb to breast cancer. These questions include: the longer-term neurotoxicity(34, 35) in the platinum and the impact of the agents in both arms on ovarian function. Little data exists regarding the effect of either capecitabine or platinum agents on ovarian function, despite increasing popularity and use. Platinum use in breast cancer includes gemcitabine + platinum [PrECOG0105] or

docetaxel + carboplatin + trastuzumab [TCH] for HER2+ breast cancer. Capecitabine use in breast or colon cancer typically occurs in the metastatic setting. In PrECOG0105, patients anecdotally reported little disruption of menses. Data for capecitabine from the colorectal world is less useful in breast cancer, due to sequencing capecitabine with agents known to disrupt ovarian functions such as anthracyclines or cyclophosphamide. Thus, due to the paucity of literature, oncologists experience difficulty counseling patients with regards to the impact of these agents on ovarian function. Ovarian function is of concern because (a) younger patients may desire to preserve fertility for child-bearing, (b) premature menopause is associated with attendant symptoms (hot flashes, sweats, vaginal dryness, decreased libido) that negatively impact HRQL.(37) and (c) premature menopause increases long term health risks (increased bone loss, possible cognitive, cardiac problems). There is an increased mortality risk with premature ovarian failure/removal in young women.(38-40)

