We hypothesize that HRQL between the groups will be superior in the platinum agent arm at the start of cycle 3 and at the 15-months after start of study treatment time-points (roughly 1 year after chemotherapy ends), and we also aim to describe the rate of neurotoxicity over time in the platinum arm, the rate of medication adherence in the capecitabine arm, and the rates of amenorrhea in both arms.

To test the primary hypothesis and assess our exploratory objectives, we have selected the following measures:

HRQL Measures. For both arms. Measures will be assessed at baseline, and start of cycle 3, as well as 6 and 15 months after the start of study treatment. These time-points have been chosen as they allow us to capture the acute difference in side-effects following receipt of chemotherapy and follow long enough to ensure that acute differences will have resolved. Differences in symptom burden and HRQL at 15 months after the start of study chemotherapy (roughly 12 months after chemotherapy ends) would be considered persistent and be considered unlikely to improve further.

- *NCCN-Fact FBSI-16 (16-items)* is a validated 16-item scale including all 8 items from the original FBSI and 8 additional items from Functional Assessment of Chronic Illness Therapy measures. The NFBSI-16 is formatted by subscale: Disease-Related Symptom, Treatment Side-Effect, and General Function and Well-Being.(41) Higher FBSI scores indicate better HRQL (score range, 0 to 16).

Ovarian Function Measure. For both arms. We will use questions used in the ATEMPT and APT studies to capture ovarian function.^{37,38} Measures will be assessed at baseline and 15 months after adjuvant study chemotherapy starts (this is roughly 12 months after chemotherapy ends). Study participants will self-report menstrual history retrospectively. Only patients aged 54 years or less at time of baseline survey will complete these questions, and we will screen out those who are not premenopausal with regular menses at diagnosis.

- *Menstrual Measures (4-items).* We will use 4 measures adapted from the ATEMPT and APT studies.³⁸ Patients aged less than 55 will be asked about (1) absence or presence of menses in the 12 months prior to neoadjuvant chemotherapy (termination of survey if no menses), (2) did they have periods at least every 2 months prior to neoadjuvant chemotherapy (termination of survey if no), (3) did they consider themselves premenopausal prior to

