neoadjuvant chemotherapy (termination of survey if no), (4) date of last menses, (5) frequency of menses over past 6 months, (6) receipt of BSO, or LHRH agonist and use of contraceptives.

Neurotoxicity Symptom Measures. For the platinum arm only. Measures will be assessed at baseline, and start of cycle 3, as well as 6 and 15 months after the start of study chemotherapy. These time-points have been chosen as they allow us to capture the baseline rate due to prior taxanes, acute development of neuropathy following receipt of platinum chemotherapy and to follow long enough to ensure that acute toxicity will have resolved. Neurotoxicity at 15 months (roughly 12 months after chemotherapy ends) would be considered persistent and unlikely to improve further.

- The *FACT-Gynecologic Oncology Group/Neurotoxicity (FACT-GOG/Ntx; 11-items)* subscale contains 11 items and is designed to assess neurotoxicity resulting from platinum and taxane-based chemotherapies. (42) Lower FACT-GOG/Ntx scores denote higher neurotoxicity (score range, 0 to 44).

Medication Adherence Measure. For the capecitabine arm only. This item will be assessed only for patients receiving capecitabine chemotherapy, and will be done twice while on study chemotherapy (start of cycle 3 and 6), to add to our understanding of why or why not a patient adhered to medication. This may yield additional insight into the primary endpoint results.

- *ECOG-ACRIN Medication Adherence Scale Modified from the Morisky Medication Adherence Questionnaire (8-items)*. This measures the likelihood that a patient will take prescribed medications. The Medication Adherence Scale has been validated against medication pill count methods of assessing compliance and used in a variety of settings. It is an 8-item measure with a Likert response scale. The minimal detectable change has been defined as 1.98 points. It will be administered to understand the reasons for non-adherence to protocol therapy.

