9.6.2 Analysis Plan for PRO Endpoints

PROs endpoints will be analyzed at the final analysis time for the primary endpoint. Any participants who take the PROs surveys at more than 1 time-point will be eligible for analysis. The primary endpoint for HRQL is FBSI TSE subscale score at 6 and 15 months after the start of chemotherapy. The primary endpoint of ovarian function is rate of amenorrhea at 15 months. Amenorrhea is defined as the absence of menses without secondary reason (e.g., pregnancy, oophorectomy or receipt of LHRH agonist, etc.) for the whole 6 months prior to the 15-month survey (i.e., no menses between 9 and 15 months). The primary analysis of HRQL will be assessed in all eligible patients. The primary analysis of rate of amenorrhea will be assessed in women aged 18-49 at enrollment who are premenopausal at cancer diagnosis.

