Subscale scores for HRQL endpoint will be prorated by multiplying the sum of the subscale by the number of items in the subscale, then dividing by the number of items actually answered: Prorated subscale score = (sum of items cores) * (number of items in subscale) / (number of items answered). When there are missing data, prorating by subscale in this way is acceptable as long as more than 50% of the items are answered in each subscale. Standard descriptive and graphical analyses will be used initially to examine missing data patterns, and to understand the relationship between variables for HRQL scores. The assessment scores for the HRQL will be compared between the two treatment arms at all time points, using two samples t test (or Wilcoxon rank sum test if the distribution of the score is not symmetric). Change in the HRQL scores between all other time points and the baseline visits will be compared between the two arms using two sample t tests. Similar analyses will be conducted for each NCCT-FACT FBSI subscales. The mean score and proportion of moderate/severe symptoms will be compared between treatment arms for each individual FBSI item at 6 months after the start of chemotherapy using Wilcoxon rank sum test and Fisher exact test, respectively, as an exploratory analysis. Mixed effect models will be constructed as another exploratory analysis to estimate the time profile of HRQL in the two treatment arms and to evaluate treatment-by-time interactions. Time will be included as a continuous variable if there is a linear trend in HRQL over time or a set of dummy variables if non-linear trend exists for HRQL. Likelihood ratio test will be used for model selection. Adjusted covariates in the mixed effect models will include patient demographic and disease characteristics, such as age, ECOG PS, clinical stage at diagnosis, residual cancer burden, prior therapy, et al.

Fisher exact test will be used to examine the difference in rates of amenorrhea between the arms at 15 months. Logistic models will be used for regression analysis for amenorrhea. Adjusted covariates in the logistic models will include patient demographic and disease characteristics, such as age, ECOG PS, clinical stage at diagnosis, residual cancer burden, prior therapy, et al.

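### The 15-month amenorrhea analysis leaves out menstrual status at Cycle 1 Day 1, so each arm's rate mixes carry-over from neoadjuvant chemotherapy with any study-drug effect and a strong baseline predictor goes unused

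*Combined protocol and SAP*

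**What the plan says.** The population is set in section 9.6.2: "The primary analysis of rate of amenorrhea will be assessed in women aged 18-49 at enrollment who are premenopausal at cancer diagnosis". Section 1.8 screens survey respondents in the same way, on menstrual history before neoadjuvant chemotherapy. Under section 3.1.4 every patient has had a neoadjuvant taxane, with or without an anthracycline, before entry.

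The outcome is no menses from month 9 to month 15: "Amenorrhea is defined as the absence of menses without secondary reason (e.g., pregnancy, oophorectomy or receipt of LHRH agonist, etc". Amenorrhea already present when study treatment starts is not among the named exceptions.

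The test is unstratified: "Fisher exact test will be used to examine the difference in rates of amenorrhea between the arms at 15 months". A logistic model is also planned, with covariates "such as age, ECOG PS, clinical stage at diagnosis, residual cancer burden, prior therapy, et al". Baseline menstrual status is not named.

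The data exist. On the ovarian function items, section 1.8 says "Measures will be assessed at baseline and 15 months after adjuvant study chemotherapy starts", and the items include "4) date of last menses, (5) frequency of menses over past 6 months, (6) receipt of BSO, or LHRH agonist and use of contraceptives". Section 7.1 places eight questions at Cycle 1 Day 1 and five at 15 months.

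Objective 2.2.6 labels the amenorrhea rates exploratory. Section 9.6.2 nevertheless makes the 15-month rate the primary endpoint for ovarian function, with a between-arm test at two-sided 5%.

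**The concern.** A woman whose periods stopped during neoadjuvant chemotherapy and never came back counts as an event at 15 months in either arm, whatever her study drug did. Section 1.8 wants to learn what platinum and capecitabine do to ovarian function, because oncologists have little to counsel patients with. It discounts the colorectal capecitabine data for a closely related reason, namely "due to sequencing capecitabine with agents known to disrupt ovarian functions such as anthracyclines or cyclophosphamide". Each arm's rate in this trial has the same difficulty: it is the cumulative result of all chemotherapy received.

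The same section of the plan treats other outcomes differently. HRQL gets a change-from-baseline comparison in 9.6.2, and section 1.8 gives the prior-taxane level as a reason for measuring neurotoxicity at baseline. Ovarian function has a baseline measurement that the analysis does not use. At stake are the interpretability of the arm-specific rates and some precision in the comparison.

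**Working it through.** **No figure to reproduce.** The documents give no sample size, expected rate, effect size or power for amenorrhea. What follows is an illustration with assumed rates.

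**Inputs from the documents.** PRO cohort 362 (9.6). Attrition 20% by 15 months (9.6.1). At least 60% premenopausal at diagnosis (1.8). Allocation 1:1 (9.2). Two-sided 5% (9.6.2).

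Women per arm: 362 × 0.80 × 0.60 / 2 = 86.9, taken as 86. This ignores the 18-49 age limit and the exclusions for secondary reasons, for which no figures are given.

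**Assumptions.** Share already amenorrheic at baseline, q = 30%, 50% or 70%. New amenorrhea among women menstruating at baseline, p = 15% versus 40%. Persistence among those already amenorrheic, s, varied below.

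**Observed rate per arm** = q·s + (1 − q)·p. With s = 70% in both arms:
- q = 30%: 0.21 + 0.105 = 31.5% versus 0.21 + 0.28 = 49.0%; difference 17.5 points
- q = 50%: 0.35 + 0.075 = 42.5% versus 0.35 + 0.20 = 55.0%; difference 12.5 points
- q = 70%: 0.49 + 0.045 = 53.5% versus 0.49 + 0.12 = 61.0%; difference 7.5 points

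The difference among women menstruating at baseline is 25 points throughout.

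**Carried-over share of all counted events** = q·s / mean rate: 0.21/0.4025 = 52%, 0.35/0.4875 = 72%, 0.49/0.5725 = 86%. Under these assumptions, most of each arm's rate says little about the study drug.

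**Power** (%, at q = 30/50/70). Fisher by exact enumeration; Mantel-Haenszel (MH) by simulation, stratified by baseline status:

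| Persistence by arm | Planned Fisher | MH, no continuity correction | MH, with correction |
|---|---|---|---|
| 70% v 70% | 60/34/14 | 73/44/19 | 67/37/14 |
| 60% v 75% | 81/72/62 | 90/82/73 | 86/78/67 |
| 50% v 75% | 90/90/90 | 95/95/94 | 93/93/92 |

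A Fisher test restricted to women menstruating at baseline (86 × 0.7 = 60, 86 × 0.5 = 43, 86 × 0.3 = 25 to 26 per arm) has power of about 83%, 68% and 38% to 41%, whatever the persistence rates. It therefore beats the planned test when the drugs do not affect recovery. It loses to it at every q when persistence is 50% versus 75%, because the planned difference is then 25 points in a larger sample.

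In these scenarios the uncorrected stratified test is always more powerful than the planned test. With continuity correction it is at least about as powerful.

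**The case against.** The strongest reply is that nothing is biased. Allocation is randomized, so women already amenorrheic are balanced between arms in expectation and the Fisher test is valid under the null. The overall rate also answers a real counselling question: of women premenopausal at diagnosis, how many have no periods about a year after all chemotherapy? This stands. A reader might infer that the plan conceals the drug effect or that the between-arm comparison is invalid. The documents do not support that; what is lost is precision and the reading of each arm's rate.

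Second, the dilution depends on assuming that the drugs do not affect recovery, which no section supports. This also stands. A reader might infer that restricting to women still menstruating would recover most of the lost power and should replace the planned analysis. That holds only under equal persistence. Where recovery differs by arm, restriction can cost power and discards part of the drug effect.

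Third, the covariate list is open-ended and includes prior therapy. In part this stands: baseline status could be added. But nothing commits to it, prior therapy is only a weak proxy, and a covariate chosen after seeing the data carries less weight.

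Fourth, the baseline classification is imperfect. Randomization may come up to 24 weeks after surgery and treatment up to 6 weeks later (3.2), so baseline may fall up to 30 weeks after surgery. The six-month look-back overlaps neoadjuvant treatment for some women and not others, and may mix temporary with lasting amenorrhea. This is a genuine limit on the fix.

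**Conclusion.** The point holds as an omission in an exploratory analysis. The population is fixed before neoadjuvant chemotherapy, menstrual status is measured again at Cycle 1 Day 1, and section 9.6.2 makes no stated use of it. As planned, neither arm's rate can be read as the ovarian effect of platinum or capecitabine.

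The precision at stake is modest and uncertain. With equal 70% persistence, stratifying raises power from about 60/34/14% to 73/44/19% without continuity correction, and to about 67/37/14% with it. These figures rest on assumed carry-over, new-amenorrhea and persistence rates and on an approximate 86 women per arm. The case for separate reporting rests on none of them. The IDFS conclusion and the HRQL comparison are unaffected.

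**What to change.** In section 9.6.2:

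1. Classify each woman at Cycle 1 Day 1 as menstruating or not since the end of neoadjuvant chemotherapy, from the date-of-last-menses and frequency items, and define how missing or ambiguous answers are handled.
2. Stratify the 15-month comparison by this status, using an exact stratified or Mantel-Haenszel test, and state whether a continuity correction applies.
3. Name the status as a covariate in the logistic model.
4. Report by arm new amenorrhea among women menstruating at baseline and recovery of menses among the others.
5. Keep the overall rate in all women premenopausal at diagnosis. Report the restricted comparison beside the overall one, not in its place.

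The cost is wording, with no new questionnaire items. Two points need confirming: that both items are among the eight baseline questions, since section 7.1 does not list them one by one, and that the end date of neoadjuvant chemotherapy is in the clinical database. The downsides are small strata and a baseline window of varying length. Tabulating the time from last neoadjuvant dose to Cycle 1 Day 1 would let readers judge the second.

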9.6.3 Tobacco Use Assessment

Detailed statistical considerations are outlined in [Appendix VI](#).

Rev. Add7

9.7 Gender and Ethnicity

Rev. Add#5

Male breast cancer accounts for approximately 1% of all breast cancers. Meanwhile, some elderly male patients may not be eligible or consider trials. We could anticipate that about 7 male patients with TNBC could enroll out of a sample size of 775, and all of them are expected to be non-Hispanic White patients. For the 768 female patients, based on previous data from SWOG S0226 and ECOG E2100 studies, the anticipated accrual in subgroups defined by gender and race is:

| Racial Categories | Ethnic Categories | | | | Total |
|---|--------------------|-------|------------------------|-------|-------|
| | Hispanic or Latino | | Not Hispanic or Latino | | |
| | Females | Males | Females | Males | |
| American Indian or Alaskan Native | 0 | 0 | 0 | 0 | 0 |
| Asian | 0 | 0 | 15 | 0 | 15 |
| Native Hawaiian or other Pacific Islander | 0 | 0 | 0 | 0 | 0 |
| Black or African American | 0 | 0 | 65 | 0 | 65 |
| White | 53 | 0 | 635 | 7 | 695 |
| Total | 53 | 0 | 715 | 7 | 775 |

The accrual targets in individual cells are not large enough for definitive treatment comparisons to be made within these subgroups. Therefore, overall accrual to the study will not be extended to meet individual subgroup accrual targets.

9.8 Study Monitoring

This study will be monitored by the ECOG-ACRIN Data Safety Monitoring Committee (DSMC). The DSMC meets twice each year. For each meeting, all monitored studies are reviewed for safety and progress toward completion. When appropriate, the DSMC will also review interim analyses of outcome data. Copies of the toxicity reports prepared for the DSMC meetings are included in the study reports prepared for the ECOG-ACRIN group meeting (except that for double blind studies, the DSMC may review unblinded toxicity data, while only pooled or blinded data will be made public). These group meeting reports are made available to the local investigators, who may provide them to their IRBs. Only the study statistician and the DSMC members will have access to interim analyses of outcome data. Prior to completion of this study, any use of outcome data will require approval of the DSMC. Any DSMC recommendations for changes to this study will be circulated to the local investigators in the form of addenda to this

protocol document. A complete copy of the ECOG-ACRIN DSMC Policy can be obtained from the ECOG-ACRIN Operations Center.

Rev. 2/16,
6/16
Rev. 9/17
Rev. Add6
Rev. Add7
Rev. Add8

10. Biological Sample Submissions

Tumor tissue from the residual disease on the definitive surgical specimen must be submitted for PAM50 analysis as defined in Section [11](#). The PAM50 analysis will be performed by the Molecular Diagnostics Laboratory (MDL) at MD Anderson Cancer Center and receipt of tumor tissue will be forwarded to the ECOG-ACRIN Operations Office and submitting institution. Results of the PAM50 analysis will not be reported to the submitting institution.

Tumor tissue will also be assessed by central review of immunohistochemistry (IHC) expression of estrogen receptor (ER), progesterone receptor (PR) and human epidermal growth factor receptor (HER2) FISH to rule out conversion of these clinical markers following chemotherapy.

Every effort should be made to submit tumor tissue specimen to the MDL immediately, as patients need to be randomized within 24 weeks from surgery.

Rev. Add8

Patients cannot proceed to STEP 1/ randomization before the EA CBPF acknowledges receipt of tumor tissue for PAM50 analysis.

Peripheral blood specimens must be submitted for defined laboratory research studies described in Section [11](#).

Rev. Add8

Peripheral blood specimen are to be submitted per patient consent for undefined future research studies.

It is required that all specimens submitted on this trial be entered and tracked using the ECOG-ACRIN Sample Tracking System (see Section [10.3](#)). An STS shipping manifest form is to be included with every submission.

All specimens must be labeled clearly with the ECOG-ACRIN protocol number (EA1131), ECOG-ACRIN patient sequence number, patient's initials, date of collection and specimen type.

Rev. Add6

10.1 Submissions to the ECOG-ACRIN Central Biorepository and Pathology Facility (CBPF)

Rev. Add7

10.1.1 Tumor Tissue Submission (**Mandatory**)

Pathology specimens must be submitted as soon as possible as not to delay randomization, as patients need to be randomized within 24 weeks from surgery.

Submitting pathologist and clinical research associate may refer to [Appendix I](#), which outlines the Pathology Submission Guidelines. Submission of pathology specimens from all patients is mandatory.

Rev. Add8

The tumor tissue specimens and pathology report are to be labeled with the Pathology accession ID number and as well as the information above.

10.1.1.1 Required Materials

Rev. Add8

Forms: Must be submitted with all tumor tissue submissions.

- STS generated shipping manifest form
- Copy of the institutional surgical pathology report

- CLIA Laboratory Sample Submission Form ([Appendix IV](#))

10.1.1.2 Pathological Material Submission:

- FFPE tumor tissue block – breast primary specimen from definitive surgery (≥ 1 cm in diameter, > minimal cellularity as per local pathologist determination).

NOTE: If these criteria cannot be met, please contact the ECOG-ACRIN CBPF ([contact]) to obtain alternative submission requirements.

